6.3.2 Efficacy Set with imputation (Efficacy Set 2)

Another efficacy set will use data imputation (LOCF) from Week 4.

If there are no efficacy data available, then the dropout would be considered as treatment failure.

6.4 PER PROTOCOL SET

The Per Protocol dataset (PP population) is defined as those patients of the FAS population without any major protocol deviation.

Major protocol deviations are defined as deviations liable to bias the evaluation of the main efficacy endpoint. The following deviations will be considered as major (non-exhaustive list):

- Noncompliance with the inclusion or exclusion criteria;
- Noncompliance with the study treatment;

- Intake of prohibited medication;
- Noncompliance with time window.

Limited programming checks e.g. prohibited medication (based on agreed codes), lab results, may be requested and reviewed on an ongoing basis. Other potential exclusions e.g. incorrect dosing of study medication may be discussed at the DRM. The final decision on inclusion in the PP Set will be agreed and documented before database lock.

7 SAFETY MONITORING

An independent Data Safety Monitoring Board (DSMB), with expertise and experience in the pathology, and without direct involvement in the conduct of the trial, will be set up specifically to guarantee effective protection of patients, ensure the ethical conduct of the trial, benefit/risk ratio of the trial, and to ensure the independent review of the scientific results during the trial and at the end of the trial. Besides, the DSMB may recommend the early termination of the trial at any time if an unacceptable toxicity occurs.

The DSMB will meet after the first 6 patients are dosed (50mg or matching placebo) for at least 2 weeks to check the 50mg dose tolerability. Once the DSMB recommendation is granted, the next 6 patients will be randomized to receive either ABX464 50mg, ABX464 100mg or placebo. A second DSMB meeting will then be held when these 6 next patients are treated for at least 2 weeks, to check the 100mg dose tolerability and grant the recommendation to resume patient's randomization.

In addition, from the first DSMB onwards, meetings will be held every month during the study period. The DSMB will also review all potential causally-related Serious Adverse Events within 7 days of the initial report.

A dose limiting toxicity (DLT) is defined as a grade 3 or higher adverse event as defined by the Common Terminology Criteria for Adverse Events (CTC-AE V5.0) considered by a safety review board as probably or definitely related to study treatment. If more than 2 DLTs occur in the first 12 treated patients for at least 14 days, then the enrolment of additional patients in the treatment group will be stopped, otherwise the enrolment of planned patients will be confirmed. In addition, in case of a life threatening (grade 4) adverse reaction enrolment in the treatment group, all treatment of ongoing patients will be immediately discontinued. In both cases, enrolment will only be resumed upon the decision of the sponsor if the Data Safety Monitoring Board can conclude that the causality of the event was unrelated or unlikely related to study treatment.

The DSMB has only a consultative role. It will inform the Sponsor who will decide whether the DSMB recommendation will be followed. A DSMB charter must be available upon submission of the trial (initial protocol) to the respective competent authorities.

The sponsor will prepare the Data Safety Monitoring Board Charter which will define the primary responsibilities of the DSMB, its relationship with other study components, its members, and the purpose and timing of its meetings. The Charter will describe the process for the evaluation of dose limiting toxicities and provide the decision criteria for study continuation.

Leading up to the meeting, the data will be extracted from the EDC Database by the Database Programmer and provided to Abivax.

8 INTERIM ANALYSES

No interim analysis is planned.

The study analysis will be performed following database lock upon the completion of the last patient or upon its early discontinuation whichever occurs first.

9 DATA

9.1 ECRF DATA

CRF data will be provided by Orion data management to the statistics department as SAS data sets in Orion standard format which will be used for programming the outputs to be included in the CSR. Populated data sets will be available when programming starts. These may contain dummy data if real data is not yet available.

9.2 EXTERNAL DATA

9.2.1 Laboratory Data

Results from Local lab will be entered in CRF for Haematology, Chemistry, Pregnancy (Serum/ urine), Thyroid (for applicable sites only) and ESR (additionally for fibrinogen, troponin I & T, prothrombin time and/or INR, depending upon CSP version they get consented to).

The following table displays the clinical laboratory parameters:

HEMATOLOGY	BIOCHEMISTRY
Hemoglobin	Sodium
Hematocrit	Potassium
WBC	Chloride
Neutrophils	Calcium
Lymphocytes	Phosphate
Monocytes	Glucose
Eosinophils	BUN or urea
Basophils	Creatinine
Platelet count	AST / SGOT
ESR	ALT / SGPT
Prothrombin time and/or INR*	Alkaline phosphatase
Fibrinogen*	GLDH
	LDH
	Lipase
	Total cholesterol
	HDL cholesterol
	LDL cholesterol
	gGT
	Total bilirubin
	Total protein
	Albumin
	CRP
	T3, T4, TSH (for French sites only)
	Troponin I & T*

Tests of TB (Quantiferon TB Gold Plus), HIV (anti-HIV Ab), HCV (anti-HCV Ab), HBV (HBsAg, anti-HBs Ab), anti-HCV Ab, will be performed only at screening. * Except at Week 1 & 2

Reference ranges will be provided by the labs before site initiation and the required parameters will be transcribed onto the Data Management Laboratory Reference Range Form by the CRA. The CRA will provide reference ranges to the DM, who will use them to verify data on CRF. Further information or language translations will be provided by the responsible CRA if required.

A negative or positive result will be counted in the tables under number of positive or number of negative values. For a parameter with only a result in the comment stated that it is inferior to a certain value (< X), all data will be flagged where there is a sign "<" to count how many data are inferior to the detection limit.

No external data transfers are scheduled for this study.

9.2.2 Other non-CRF data

There will be no other non-CRF data.

9.3 RANDOMISATION LIST

The randomisation list will be uploaded to a SAS dataset following database lock.

9.4 PROGRAMMING AND DATA REVIEW

Programming of analysis datasets, tables, figures and listings will be ongoing during the data management of the study. Outputs for the DSMB will be reviewed, but not fully QCd. Blind outputs may be reviewed by ABIVAX before DBL.

When the final data is considered clean, key listings (to be agreed) will be run and distributed to the study team for review. A blind data review meeting will be held to discuss the outcome of this review, the imputations for the primary endpoint and the protocol deviations. Once all data issues have been resolved and the analysis populations approved, the database will be locked. The final run of outputs and quality control (QC) will then take place.

A Data Review Meeting (DRM) may be held at the discretion of the Client. During this meeting, data listings (agreed in advance and provided by Simbec-Orion a few days before the meeting) will be used to review any outstanding problematic cases where evaluability of the data is unclear. The populations of patients for the statistical analysis and reporting of the study will be agreed and recorded by the study Statistician.

The study Data Manager, Statistician or Statistical Programmer, Project Manager and a Medic of Simbec-Orion will attend the DRM with representatives of Abivax.

10 STATISTICAL METHODS

10.1 GENERAL PRINCIPLES

All statistical methods will be based on the International Conference on Harmonisation (ICH) E9 document "Statistical Principles for Clinical Trials".

Data will be summarised by treatment group. A total column showing all patients will be included for baseline and safety summaries. Where appropriate, data will also be summarised by visit with summaries for each visit attended as scheduled and an additional summary for final (last scheduled visit or early withdrawal). The format of the summaries is defined in the shells at the end of this document.

In summary and analysis tables of continuous variables, standard descriptive statistics (N, mean, standard deviation [SD], median, minimum and maximum) will be presented. Least squares mean (LS mean), standard error (SE) and 95% confidence interval (CI) will be presented in the statistical analysis outputs as appropriate. For PK summaries, arithmetic mean (AM), geometric mean (GM) and coefficient of variation (%CV) will be used to summarise the data. The minimum and maximum statistics will be presented in summary tables to the same number of significant figures as the original data. The mean/AM, median, LS mean, GM, CI, SD and SE will be presented to one more significant than the original data.

For numeric data which includes non-numeric values (e.g. PK data reported as Below Limit of Qualification (BLQ) or lab results reported as < 10 or >100) the following principles will be applied when summarising the data:

- BLQ will be replaced with a value that is ½ of the lower limit of quantification (LLQ);
- Results reported as < x will be treated in the same way as BLQ with LLQ=x;
- Otherwise AM, GM, SD, CI and %CV will not be calculated;
- Whenever meaningful, minimum, median and maximum will be presented based on the reported data (e.g. minimum = <10, median = 20, maximum = >100).

In summary tables of categorical variables, the number of non-missing observations by category will be presented with percentages. The number of missing observations will also be presented when non-zero. Unless otherwise specified, the denominator for each percentage will be the number of non-missing observations within the column. All percentages will be presented to one decimal place.

Patient line plots will use actual time on the time axis. Mean plots will use a linear time scale for the nominal times of the visits and will be labelled by visit. Results from an early withdrawal visit will be excluded.

If changes in severity for the same TEAE have been reported separately but with the same AE number, they will be collapsed to a single AE with maximum severity for the summary tables, but listed as reported.

Classifications of medical history, concomitant medication and adverse events will be sorted alphabetically within the summary tables.

If any laboratory assessments are repeated at the same visit, the result from the repeat assessment will be used in summaries. Both values will be listed.

CRF data collected/ Data collected on the eCRF will be presented within data listings. The data listings will be sorted by treatment group, country, centre number, patient number and visit/week/day. Treatment group will be as allocated (randomised). If any patients receive the wrong treatment this will be flagged in all listings. Visits outside the visit windows will be identified within the listings. For patients who complete the study, the last visit will be described in the listings as '<Day X>'; for those who withdraw early it will be described as 'End of Study'.

The date format for all output presentations will be 'ddMMMyyyy'.

All statistical analysis will be performed using SAS 9.2 or higher.

All hypothesis testing will be carried out at the 5% (2-sided) significance level unless stated otherwise.

P-values will be rounded to four decimal places. P-values less than 0.0001 will be reported as <0.0001 in tables.

If any of the assumptions underlying the formal statistical methods proposed are violated during the analysis of the final data, alternative statistical methods will be used and any changes documented in the statistical methods section of the clinical study report (CSR), including the rationale for use.

10.2 STRATIFICATION AND COVARIATE ADJUSTMENT

Randomization will be stratified according to a single factor: patients without previous exposure to anti-TNF α therapy versus patients with previous exposure to anti-TNF α .

10.3 INTERACTIONS

The interaction between treatment in two different doses and placebo will be investigated for the primary endpoint (incidence of treatment-emergent adverse events categorized by severity).

10.4 MISSING DATA

For total scores and subscales with missing items the following rule will be used:

If < 50% of the scale items are missing, the total (or subscale total) will be calculated using the mean score of the non-missing items for that scale or subscale to impute a score for the missing items. In practice the score is derived using the formula:

$$\text{total of non-missing items} \times \text{number of items in (sub)scale} / \text{number of non-missing items}$$

If > 50% of the items were missing, no scale or subscale score will be calculated; the score will be considered missing.

There will be no other imputation of missing data in this study.

10.5 POOLING OF SITES

Sites will be pooled for all analyses. There will be no adjustment for centre effect or treatment by centre interaction.

10.6 MULTIPLE COMPARISONS

There will be no corrections to nominal p-values for multiple comparisons because the results of the tests will be interpreted in a descriptive manner.

10.7 SUBGROUP ANALYSES

Not applicable.

10.8 STATISTICAL ISSUES

Not applicable.

11 STATISTICAL OUTPUT

General principles for layout of the statistical output are described in Section 10.1, including specification of the table columns, and these are illustrated for each unique table in the table shells in Section 15. For clarity and brevity in this document the phrase “by treatment group” is understood for all summaries and is not included within the text of this section.

11.1 PATIENT DISPOSITION

A summary of the number of screened patients, baseline failures, screening failures and reasons for screening failure will be produced for all enrolled patients (*Table 14.1.1*). The patient disposition table (*Table 14.1.2*) will summarise the following data for all randomised patients:

- The number (%) of patients in the FAS,
- The number (%) of patients in the Safety Set,
- The number (%) of patients in the PP Set.

The number (%) of patients who withdraw from the study and the main reason for withdrawal will be summarised. (*Table 14.1.3*)

A listing of all patients with protocol deviations will be presented. A data listing presenting the eligibility for the analysis sets for each patient will also be presented.

11.2 PATIENT CHARACTERISTICS AT BASELINE

11.2.1 Demographic and Baseline Characteristics

Demographics and other baseline characteristics will be summarized by treatment arm (*Table 14.1.4*). This analysis will be conducted on the FAS population.

Age will be calculated using Date of Birth (DOB) and Date of first treatment (Visit 1) and presented as age at last birthday as an integer.

BMI is the patient’s body weight in kilograms divided by the square of the patient’s height in metres.

11.2.2 Medical History and Current Medical Conditions

All conditions will be coded using the version 23.0 of the Medical Dictionary for regulatory Activities (MedDRA) defined in the Data Management Plan. Past medical/surgical history and current medical conditions will be summarised by system organ class (SOC) and preferred term (PT). The number (%) of patients reporting each condition will be presented using the FAS (*Table 14.1.5.1 and 14.1.5.2*).

11.3 EFFICACY ANALYSES

Analysis of efficacy data will be carried out on Efficacy Set 1 and will be repeated for Efficacy Set 2. Treatment comparisons will be ABX464 in two different doses vs. placebo.

11.3.1 Primary Variable

The primary efficacy endpoint of the study, the ACR20 response rate, will be compared in subjects who received a given dose of ABX464 or placebo by likelihood ratio chi-square test on a 10% two-sided level (Table 14.2.1.1 and Table 14.2.1.2).

The result of the test will be interpreted in a descriptive manner therefore no adjustment for multiple comparison is applied.

11.3.2 Secondary Variables

Descriptive statistics will be presented by treatment arm for all secondary efficacy variables for each measurement timepoints separately for the study groups:

- Proportion of patients achieving a categorical ACR20 response at Week 12 (Table 14.2.2.1 and Table 14.2.2.2).
- Change from Baseline in the individual components of the ACR20 response at Week 2, Week 4, Week 8 and Week 12 (Table 14.2.3.1 and Table 14.2.3.2):
 - C-Reactive Protein (CRP) (mg/L),
 - Tender/painful joint count (TJC) (28 joints),
 - Swollen joint count (SJC) (28 joints),
 - Patient assessment of joint pain (Pain-VAS),
 - Patient global assessment of disease (PtGA),
 - Physician's Global Assessment of Disease (PrGA),
 - HAQ-DI.
- Change from Baseline in the following disease parameters at Week 2, Week 4, Week 8 and Week 12:
 - ESR (Table 14.2.4.1.1 and Table 14.2.4.1.2);
 - DAS28-CRP (Table 14.2.4.2.1 and Table 14.2.4.2.2) and DAS28-ESR (Table 14.2.4.3.1 and Table 14.2.4.3.2);
 - SDAI score (Table 14.2.4.4.1 and Table 14.2.4.4.2);
 - CDAI score (Table 14.2.4.5.1 and Table 14.2.4.5.2);
 - FACIT-Fatigue score (Table 14.2.4.6.1 and Table 14.2.4.6.2).
- Proportion of patients achieving:
 - ACR20/50/70 response;
 - Categorical DAS28-CRP response;
 - LDA;
 - DAS28-ESR remission;
 - ACR/EULAR remission;
 - SDAI remission;
 - CDAI remission
 at Week 2, Week 4, Week 8 and Week 12 (Table 14.2.5.1 and Table 14.2.5.2).

These statistics include:

- Continuous variables: mean, standard deviation, minimum and maximum, stratified 95% confidence intervals, median and quartiles will be presented.
- Categorical variables: counts, rates and stratified 95% confidence intervals for the rates will be calculated.

In addition to descriptive statistics, mixed model analysis of covariance will be conducted for the following measurements:

- The change from baseline in DAS28-CRP and DAS28-ESR;
- The change from baseline in the individual components of the ACR20 response (CRP, TJC(28), SJC(28), Pain-VAS, PtGA, PrGA, HAQ-DI) and in ESR;
- The change from baseline in SDAI and CDAI scores.

In this model, treatments and stratum will be fixed effects, subjects will be random effect, and baseline values of the respective measurements will be covariates. Other explanatory variables will also be allowed to be included in the model. In order to normalize eventual skewed distributions transformation of the data will also be considered. Study groups will be compared within this model framework. All p-values will be interpreted in a descriptive manner.

All other analyses will be descriptive.

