Intervention/treatment Active Arm											
Group #1 (n=20): 100mg qd	2 capsules of 50mg ABX464										
Group #2 (n=20): 50mg qd	1 capsule of 50mg ABX464 + 1 capsule of matching placebo										
Group #3 (n=20): Placebo	2 capsules of matching Placebo										

Study n° ABX464-301
	
Clinical Phase IIa Type of Study Safety, Tolerability, Efficacy Study

	
approvals.
 
In the present study (ABX464-301), randomization will be stratified according to a single factor: patients without previous exposure to anti-TNFα therapy versus patients with previous exposure to anti-TNFα therapy.
 
Study scheme:
 

Study Objectives
	
Primary Objective
 
The primary objective of the study is to evaluate the safety of ABX464 given at two different doses (100mg and 50 mg) vs placebo in combination with MTX when administered once daily in patients with moderate to severe active Rheumatoid Arthritis.
 
Secondary Objectives
 
The secondary objectives are:
 
 ▪ To evaluate the effects of the different dose groups of ABX464 at Week 2, Week 4, Week 8 and Week 12 on the American College of Rheumatology (ACR) 20/50/70 response and each of its components versus placebo; ▪ To evaluate the effects of the different dose groups of ABX464 at Week 2, Week 4, Week 8 and Week 12 on disease activity scores (DAS28 scores, simplified disease activity score [SDAI] and clinical disease activity score [CDAI]) versus placebo; ▪ To evaluate the effects of the different dose groups of ABX464 at Week 2, Week 4, Week 8 and Week 12 on clinical response (DAS28 EULAR good and moderate responses), Low Disease Activity (LDA) or remission (DAS28-ESR remission, ACR/EULAR remission, SDAI and CDAI remission) versus placebo; ▪ To evaluate the effects of the different dose groups of ABX464 at Week 2, Week 4, Week 8 and Week 12 on the Patient Reported Outcomes (PRO), Healthy Assessment Questionnaire – Disability Index (HAQ-DI) and Functional Assessment of Chronic Illness Therapy (FACIT)-Fatigue; ▪ To evaluate the expression of miR-124 in total blood (determined by qPCR) at baseline and Week 8 ▪ To evaluate the effect of the different dose groups of ABX464 at Week 8 on miR-124 expression in total blood versus placebo; ▪ To assess the pharmacokinetics of the ABX464 and its main active metabolite N-Glu-ABX464 after oral administration of different daily doses of ABX464 in patients with Rheumatoid Arthritis.

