8.2. Efficacy Analysis

Analysis of efficacy data will be carried out in the Full Analysis Set in which subjects who prematurely terminate the study will be considered failures.

The primary efficacy endpoint of the study, the ACR20 response rate, will be compared in subjects who received a given dose of ABX464 or placebo by likelihood ratio chi-square test on a 10% two-sided level.

The result of the test will be interpreted in a descriptive manner therefore no adjustment for multiple comparison is applied.

In addition, descriptive statistics will be presented by treatment arm for all secondary efficacy variables for each measurement timepoints separately for the two study groups.

These statistics include:

- Continuous variables: mean, standard deviation, minimum and maximum, stratified 95% confidence intervals, median and quartiles will be presented.
- Categorical variables: counts, rates and stratified 95% confidence intervals for the rates will be calculated.

In addition to descriptive statistics, mixed model analysis of covariance will be conducted for the following measurements:

- The change from baseline in DAS28-CRP and DAS28-ESR
- The change from baseline in the individual components of the ACR20 response (CRP, TJC(28), SJC(28), Pain-VAS, PtGA, PrGA, HAQ-DI) and in ESR
- The change from baseline in SDAI and CDAI scores
- The change from baseline in miR-124 in total blood at Week 8

In this model, treatments and stratum will be fixed effects, subjects will be random effect, and baseline values of the respective measurements will be covariates. Other explanatory variables will also be allowed to be included in the model. In order to normalize eventual skewed distributions transformation of the data will also be considered. Study groups will be compared within this model framework. All p-values will be interpreted in a descriptive manner.

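### FACIT-Fatigue is the only change-from-baseline disease measure in SAP 11.3.2 without a prespecified baseline- and stratum-adjusted comparison with placebo, although a synopsis objective names it

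*SAP*

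**What the plan says.** **Objective.** The synopsis has a secondary objective on the effects of the dose groups at Weeks 2, 4, 8 and 12 on two instruments, HAQ-DI and "Functional Assessment of Chronic Illness Therapy (FACIT)-Fatigue". Protocol 2.2 and SAP 2.2 carry the same objective with HAQ-DI alone. Change from baseline in FACIT-Fatigue at those four visits is a secondary endpoint in the synopsis, Protocol 2.4 and SAP 4.2.2.

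**Model.** The change-from-baseline list in SAP 11.3.2 ends with "FACIT-Fatigue score (Table 14.2.4.6.1 and Table 14.2.4.6.2". The section then states: "In addition to descriptive statistics, mixed model analysis of covariance will be conducted for the following measurements". The list has three entries:
- "The change from baseline in DAS28-CRP and DAS28-ESR"
- the ACR20 components and ESR: "CRP, TJC(28), SJC(28), Pain-VAS, PtGA, PrGA, HAQ-DI) and in ESR"
- the SDAI and CDAI scores

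Treatment and stratum are fixed effects, subject is random, and the baseline value is a covariate. The section continues "Study groups will be compared within this model framework" and ends "All other analyses will be descriptive".

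**Protocol.** The synopsis methods and Protocol 8.2 have the same three entries, including "The change from baseline in SDAI and CDAI scores", plus miR-124. Neither names FACIT-Fatigue.

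**Output.** The SAP titles the FACIT-Fatigue tables (14.2.4.6.1 and 14.2.4.6.2) as summaries and gives them their own shell. It shows N, mean, stratified 95% CI, SD, range, median and quartiles for each arm. The ESR, DAS28, SDAI and CDAI tables are titled as analyses and also have an ANCOVA row and a p-value column.

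**The concern.** FACIT-Fatigue has the same visits and the same type of endpoint as the modelled scores, and a baseline value is collected. SAP 5.2.11 gives its scoring and its missing-item rule. HAQ-DI, its partner in the synopsis objective, is modelled. Neither document says why fatigue is handled differently.

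Readers will still compare fatigue across arms, because the synopsis asks about the effect of the dose groups. With about 20 patients per arm, chance differences in baseline fatigue can be sizeable, and the by-arm change scores do not correct for them. For every other change score in the section, the plan fixes an adjusted comparison in advance. For fatigue, any adjusted comparison would have to be chosen after the data are seen.

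**Working it through.** **Step 1. Compare the two lists in SAP 11.3.2.**
- Change-from-baseline measures: 7 ACR components + ESR + DAS28-CRP + DAS28-ESR + SDAI + CDAI + FACIT-Fatigue = 13.
- Measures in the model: 2 (DAS28-CRP, DAS28-ESR) + 7 (ACR components) + 1 (ESR) + 2 (SDAI, CDAI) = 12.
- 13 − 12 = 1, and the one missing is FACIT-Fatigue.

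miR-124 is modelled in Protocol 8.2 but not in the SAP. It is a biomarker and is not on the 11.3.2 change list, so the count is unaffected.

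**Step 2. Check whether another provision supplies the comparison.** SAP 11.3 says in general that comparisons are each dose against placebo, but attaches no method or table to fatigue. The closing sentence of 11.3.2 makes everything outside the model descriptive. The FACIT-Fatigue shell has no ANCOVA row, p-value or difference column, and its stratified CIs are within-arm. No adjusted comparison is specified anywhere.

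**Step 3. What can be recovered from the planned tables.** From the by-arm N, mean and SD of change, a reader can form

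difference = mean(dose) − mean(placebo), SE = √(SD₁²/n₁ + SD₀²/n₀).

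This is a valid unadjusted contrast under randomisation. It uses neither the baseline values nor the stratum.

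**Step 4. Size of the gain, as illustration.** The documents give no SD, effect size or correlation for FACIT-Fatigue, so there is no plan figure to reproduce. The plan's stated power concerns ACR20 and TEAE rates and plays no part here. Assumptions: equal variance s² at baseline and follow-up, correlation r between them, one visit, stratum ignored, 20 per arm.
- Raw change: variance per patient = 2(1 − r)s².
- Baseline-adjusted: variance per patient = (1 − r²)s².
- Ratio = (1 − r²) / [2(1 − r)] = (1 + r)/2.
- Half-width of the 95% CI for an arm difference, in units of s: 1.96 × √(variance × 2/20).

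| r (assumed) | Variance ratio | Variance saved | CI width ratio | Half-width, raw change | Half-width, adjusted |
|---|---|---|---|---|---|
| 0.5 | 0.75 | 25% | √0.75 = 0.87 | 0.62 | 0.54 |
| 0.7 | 0.85 | 15% | √0.85 = 0.92 | 0.48 | 0.44 |

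The interval narrows by about 13% at r = 0.5 and 8% at r = 0.7. A lower correlation gives a larger gain against raw change: at r = 0.3 the half-width goes from 0.73 to 0.59.

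**The case against.** The strongest defence is that the plan is consistent. FACIT-Fatigue is outside the model in the synopsis methods, Protocol 8.2 and SAP 11.3.2, and the separate title and shell suggest a deliberate choice. The study tests no formal hypothesis, all p-values from this model are descriptive, and a phase IIa sponsor may choose which secondary outcomes to model. This stands, and it limits the point to an improvement. It gives no reason for the exception, and it leaves the synopsis objective at odds with Protocol 2.2 and SAP 2.2.

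Four stronger readings are tempting, and the documents do not support them.
- *The SAP departs from the protocol's model.* For FACIT-Fatigue it does not. The one protocol-SAP difference in this list is miR-124, which is a separate matter.
- *Fatigue gets no between-arm information.* The planned tables allow an unadjusted difference and show baseline means by arm. Only the prespecified adjusted comparison is missing.
- *Half of the patient-reported outcomes go unmodelled.* The synopsis objective names two instruments, but Pain-VAS and PtGA are also patient-reported and are in the model. With HAQ-DI, three of these four are modelled.
- *FACIT-Fatigue was dropped from the objectives in Protocol 2.2 and SAP 2.2.* The texts differ, but nothing shows which is intended. The synopsis bullet also lacks the explicit reference to placebo found in the efficacy objectives before it.

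The gain in Step 4 is generic and modest, and it rests on an assumed correlation. That criticism is fair.

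**Conclusion.** The point holds as an inexpensive improvement. FACIT-Fatigue is the only one of 13 change-from-baseline disease measures in SAP 11.3.2 without the baseline- and stratum-adjusted comparison, and the synopsis names it in a secondary objective. The consequence is limited to one descriptive secondary endpoint and does not affect error control, the primary safety analysis or ACR20.

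The count of 12 out of 13 comes straight from the text. The precision gain of 15-25% in variance, or about 8-13% in interval width, depends on the assumed equal variances and r of 0.5 to 0.7, and no trial-specific figure can be computed. Protection against chance baseline imbalance at about 20 per arm is a further reason to adjust.

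**What to change.** 1. Add change from baseline in FACIT-Fatigue to the mixed-model lists in SAP 11.3.2, Protocol 8.2 and the synopsis methods.
2. Give Tables 14.2.4.6.1 and 14.2.4.6.2 an ANCOVA section showing the LS mean difference with 95% CI for each dose against placebo at each visit. Copying the Table 14.2.4.1.1 layout is not enough: it adds an ANCOVA row with a p-value, but no difference, no interval and no separate result for each dose. SAP 10.1 mentions LS means, SEs and CIs only where appropriate.
3. Reconcile the patient-reported-outcome objective between the synopsis and Protocol 2.2 / SAP 2.2. If fatigue is meant to stay descriptive, say so and give the reason.

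The cost is one more outcome in an existing program, with no new data collection. If each contrast carries a p-value, that adds 2 doses × 4 visits = 8 descriptive p-values per efficacy set, or 16 over the two sets. SAP 10.6 already leaves p-values unadjusted because the tests are read descriptively.
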